1.3 Rationale

Pazopanib is FDA approved as a second line and beyond treatment for metastatic soft tissue sarcoma. There is a population of elderly and debilitated soft tissue sarcoma patients that are not fit for standard first line chemotherapy that is doxorubicin based. As pazopanib is well tolerated with minimal side effects, we propose a phase II study to evaluate pazopanib as a first-line agent in patients with non-resectable or metastatic disease who are not candidates for cytotoxic chemotherapy.

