1.4 Background of Correlative Studies

Sleijfer et al. recently published a translational study in which they evaluated whether cytokine levels in the patients enrolled in EORTC 62043, the phase II study of pazopanib in soft tissue sarcoma, correlated with PFS and OS. They measured levels of several cytokines at baseline and 12 weeks after beginning pazopanib therapy and demonstrated that baseline levels were not predictive, but that high sVEGFR2 and low PIGF were associated with a more favorable PFS at 12 weeks (OR 0.636, 95% CI 0.413-

0.977, P=0.039) and (OR 1.081, 95% CI 1.007-1.160, P=0.0318) respectively. There was also a trend toward high sVEGFR2 at week 12 and increased OS and a statistically significant association between low PIGF levels at week 12 and longer OS (HR 1.061, 95% CI 1.025-1.099, P=0.0009) ⁶.

We propose to measure sVEGFR2 and PIGF levels at baseline, 4 weeks, 8 weeks, and 12 weeks to both verify the results of Sleijfer et al and to determine if there is an even earlier correlation that can be detected between levels of these cytokines and PFS as well as OS which may allow us to better predict treatment response early on in therapy

In addition, plasma pazopanib concentrations will be determined immediately prior to the first dose of each dose escalation, then after steady-state is reached at 800 mg QD (after at least 10 days of 800 mg QD administration). These PKs will only be performed in the first 10-20 patients enrolled at Washington University.

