2.2 Secondary Objectives

1. To determine the rate of progression-free survival (PFS) in patients with soft tissue sarcoma not candidates for chemotherapy treated with first-line pazopanib.
2. To determine the rate of overall survival (OS) in patients with soft tissue sarcoma not candidates for chemotherapy treated with first-line pazopanib.
3. To evaluate the quality of life of patients with soft tissue sarcoma not candidates for chemotherapy treated with first-line pazopanib.
4. To correlate serum sVEGFR2 and PICG levels with outcomes.

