3.0 PATIENT SELECTION

3.1 Inclusion Criteria

1. Histologically confirmed diagnosis of nonresectable or metastatic soft tissue sarcoma. The following histologies are excluded: embryonal rhabdomyosarcoma, chondrosarcoma, osteosarcoma, Ewing tumors, primitive neuroectodermal tumors, gastrointestinal stromal tumors, dermatofibrosarcoma protuberans, inflammatory myofibroblastic sarcoma, and mixed mesodermal tumors of the uterus.

2. Evaluable disease by imaging or physical exam OR measurable disease defined as at least one lesion that can be accurately measured in at least one dimension (longest diameter to be recorded) as ≥ 10 mm with CT scan, as ≥ 20 mm by chest x-ray, or ≥ 10 mm with calipers by clinical exam.
3. Not a candidate for chemotherapy as determined by the treating physician.
4. Age ≥ 18 years
5. ECOG performance status ≤ 2 (see Appendix A).
6. Normal bone marrow and organ function as defined below:
 - a. Absolute neutrophil count $\geq 1,500/\text{mcl}$
 - b. Platelets $\geq 100,000/\text{mcl}$
 - c. Hemoglobin ≥ 9.0 g/dL
 - d. PT or INR $\leq 1.2 \times$ IULN (if not receiving anticoagulation therapy)
 - e. PTT $\leq 1.2 \times$ IULN (if not receiving anticoagulation therapy)
 - f. Total bilirubin $\leq 1.5 \times$ IULN or $\leq 3.0 \times$ IULN with normal AST and ALT in patients with Gilbert's disease
 - g. AST(SGOT)/ALT(SGPT) $\leq 2.5 \times$ IULN
 - h. Creatinine ≤ 1.5 mg/dL OR creatinine clearance ≥ 30 mL/min/1.73 m² for patients with creatinine levels above 1.5 mg/dL
 - i. UPC < 1 (in like units) or, if UPC ≥ 1 , 24-hour urine protein < 1 g; use of urine dipstick for renal function assessment is not acceptable.

Notes:

Subjects may not have had a transfusion within 7 days of screening assessments. Concomitant elevation of bilirubin and AST/ALT above the IULN is not allowed.

Patients receiving anticoagulation therapy are eligible if their INR is stable and within the recommended range for the desired level of anticoagulation.

7. Ability to swallow and retain oral tablets.
8. Women of childbearing potential must agree to use adequate contraception (hormonal or barrier method of birth control, abstinence) prior to study entry and for the duration of study participation. Should a woman become pregnant or suspect she is pregnant while participating in this study, she must inform her treating physician immediately.
9. Ability to understand and willingness to sign an IRB approved written informed consent document.

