15.0 STATISTICAL CONSIDERATIONS

15.1 Sample Size

This is a single arm phase II trial. A single-stage design requires a total of 56 eligible patients to be enrolled in order to provide 81.64% power to test the desired 16 week clinical benefit rate (CBR) > 35% against an unfavorable CBR < 20% based on the exact binomial method at 5% significance level (actual significance level = 4.32%). Clinical benefit rate is defined as CBR = CR + PR + SD lasting \geq 16 weeks. If 17 or more patients benefit at the end of the trial, the treatment regimen yields a higher clinical benefit rate and warrants further investigation.

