15.2 Statistical Analysis

Clinical benefit rate will be calculated with 95% confidence interval (CI) based on the Wilson score method and compared to the pre-specified unfavorable CBR of 20% based on one-sided exact binomial test. The serum levels of sVEGFR2 and PIGF at each time point will be plotted and Pearson or Spearman's correlation coefficient will be calculated to explore their relationship. PFS and OS in the overall cohort of patients and by dichotomized sVEGFR2, PIGF and their combinations at each time point will be

analyzed and plotted by the Kaplan-Meier method with 95% CI. PFS and OS probabilities, overall and by group will be reported with 95% CI at desired time point. Cox proportional hazard model will be used to report resulting hazard ratio and Wald test P-values on sVEGFR2 and PIGF in continuous format.

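### The biomarker Cox models name no covariate beyond sVEGFR2 and PlGF, so they cannot show whether a marker adds prognostic information to baseline ECOG status, which is already recorded

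*Combined protocol and SAP*

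**What the plan says.** Secondary objective 4 in Section 2.2 is "To correlate serum sVEGFR2 and PICG levels with outcomes" (PICG is evidently PlGF). Section 1.4 gives the schedule, "We propose to measure sVEGFR2 and PIGF levels at baseline, 4 weeks, 8 weeks, and 12 weeks", and the purpose: to verify an earlier cytokine study and to look for an earlier correlation with PFS and OS, "which may allow us to better predict treatment response early on in therapy".

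Section 15.2 holds the whole survival analysis of the markers. It has Kaplan-Meier curves by dichotomised marker, and then: "Cox proportional hazard model will be used to report resulting hazard ratio and Wald test P-values on sVEGFR2 and PIGF in continuous format". No adjustment covariate, stratification factor or multivariable model appears there or elsewhere in the document.

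On performance status, Section 3.1 requires "ECOG performance status ≤ 2 (see Appendix A", so grades 0, 1 and 2 can all be enrolled. The Section 10.0 calendar records it at screening, on day 1 of each cycle and at end of treatment. Section 1.3 describes the target group: "There is a population of elderly and debilitated soft tissue sarcoma patients that are not fit for standard first line chemotherapy".

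**The concern.** A marker helps early prediction if it adds to what is already known at the bedside, and performance status is known before the first dose. In a cohort described as elderly and debilitated, with ECOG from 0 to 2, a cytokine level may partly reflect general condition. If general condition also affects PFS and OS, a model containing the markers alone gives a hazard ratio that mixes the marker's own contribution with that of performance status. The report could then present a marker as useful for prognosis when it only repeats the ECOG grade. The plan has no model that would tell these two cases apart, although the data needed are already collected.

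**Working it through.** **The plan's own figures.** The documents give no sample size, event count or power for the Cox models. The only design calculation is for the primary endpoint: "A single-stage design requires a total of 56 eligible patients to be enrolled", with success at 17 or more. Exact binomial tails give P(X≥17 | 56, 0.20) = 4.32%, as stated, and P(X≥17 | 56, 0.35) = 80.64%. The plan states "81.64% power to test the desired 16 week clinical benefit rate (CBR) > 35"%, one point higher and possibly a digit slip. This has no bearing on the present point. From here only n = 56 is used.

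**Inputs that are assumptions, not document figures:** the ECOG distribution, the hazard ratio for ECOG, the marker-ECOG relation, the event fraction, and no marker effect given ECOG.

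**Set 1: ECOG in two levels.** 40% of patients have ECOG 2. Survival is exponential and 90% have events (0.9 × 56 = 50.4). The marker mean is shifted by δ SD in ECOG 2 patients. Each simulated trial is analysed by Cox regression with a two-sided Wald test at 5%, on the marker alone and then on marker plus ECOG 2. The simulation was run three times. Unadjusted ranges cover all three runs; adjusted ranges cover the two with exact figures, and the third gave 5% to 6%.

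| ECOG 2 hazard ratio | Shift δ | p<0.05, marker alone | p<0.05, with ECOG |
|---|---|---|---|
| 1.5 | 0.3 SD | 5.7-5.9% | 5.4-6.1% |
| 2.0 | 0.5 SD | 8.0-8.9% | 5.3% |
| 2.5 | 0.8 SD | 16.6-17.8% | 5.5-5.9% |

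**Hand check of the middle row.** The SD of the ECOG 2 indicator is √(0.4 × 0.6) = 0.490. Taking δ in within-group SD units, the implied correlation is ρ = 0.5 × 0.490 / √(1 + 0.25 × 0.24) = 0.238. The induced log hazard ratio per marker SD is about ln(2.0) × ρ × 0.490 = 0.693 × 0.238 × 0.490 = 0.081, a hazard ratio of 1.08, as simulated. With standard error about 1/√50.4 = 0.141, the Wald statistic is centred near 0.081/0.141 = 0.57. The chance of exceeding 1.96 in absolute value is then about 8.8%, in line with the table. The same formula gives ρ of about 0.15 and 0.37 for the first and last rows.

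**Set 2: graded ECOG, as a sensitivity check.** ECOG 0/1/2 is 25/45/30%, median OS is 12 months at ECOG 1, censoring is at 36 months (about 48 deaths), and there are 1,000 runs per setting. The adjusted model uses the ECOG grade as a linear term.

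| Marker-ECOG correlation | Marker alone, HR 1.5 per grade | Marker alone, HR 2.0 per grade | With ECOG (both HRs) |
|---|---|---|---|
| 0 | 5.8% | 5.5% | 5.1-6.4% |
| 0.2 | 7.1% | 9.9% | 5.2-5.7% |
| 0.3 | 10.8% | 15.0% | 5.5-6.9% |
| 0.4 | 11.3% | 24.4% | 5.1-5.3% |
| 0.5 | 17.0% | 36.1% | 4.9-5.4% |

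For correlations of 0.2 to 0.5, the unadjusted hazard ratio per SD runs from 1.06 to 1.29; with adjustment it stays within 0.99 to 1.01. The upper rates exceed those of set 1 because a hazard ratio of 2.0 per grade means 2.0² = 4.0 between ECOG 0 and 2, a strong assumption. Set 2 does not test how well a two-level ECOG term would do if risk also differs between grades 0 and 1.

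**Feasibility.** About 48 deaths over three terms (two markers and ECOG) is 48/3 = 16 events per term, if all 56 patients contribute a sample.

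**The case against.** The strongest reply is that the plan answers the question it asks. Objective 4 is to correlate marker levels with outcomes, and an unadjusted hazard ratio does that. If marker and ECOG are related and ECOG drives survival, the marker really is associated with survival, so a small p-value is a correct finding about marginal association. A marker can also predict without being independent of performance status. This stands. A reader might infer from the tables that the planned Wald tests have an inflated type I error. They do not, for the hypothesis that Section 15.2 implies. The rates above are error rates only for the different hypothesis of no marker effect given ECOG.

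It also stands that no passage links either cytokine to performance status or gives an ECOG effect on survival, so the size is conditional throughout. Section 15.2 names no other covariate but does not forbid one. ECOG is not the only candidate: Section 3.1 leaves unsuitability for chemotherapy to the treating physician, and Section 1.1 mentions age, comorbidity and some 70 histologies. The case for ECOG is that it is graded, recorded at screening for every patient, and closest to the frailty described in Section 1.3.

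Finally, no decision rests on these p-values. Two markers, four time points and two outcomes would make 2 × 4 × 2 = 16 tests, of which 16 × 0.05 = 0.8 would be significant by chance if no association existed. That keeps the point minor. It does not supply the missing adjusted estimate.

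**Conclusion.** The point holds as a minor gap in a secondary analysis. The planned models describe marginal association validly but cannot show whether sVEGFR2 or PlGF adds to baseline ECOG, which the aim in Section 1.4 calls for.

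In the set 1 scenarios, a marker with no effect given ECOG reaches p<0.05 in about 6% to 17% of trials unadjusted, against about 5% to 6% adjusted. The weakest scenario shows no material difference. The stronger graded assumptions reach 36%, and zero correlation gives no inflation. All of this depends on a marker-ECOG relation and an ECOG effect that the documents do not give.

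A reader might also infer that an adjusted hazard ratio would establish predictive value. It would not. With a single arm, even the adjusted model can show only prognostic value beyond performance status, not prediction of benefit from pazopanib. Nor does adjustment deal with markers taken at weeks 4 to 12 when PFS is counted from the start of treatment (Section 12.4.5). The primary clinical benefit test is unaffected.

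**What to change.** In Section 15.2, pre-specify for each PFS and OS Cox model a supportive version that adds baseline ECOG (0-1 vs 2). Report it beside the unadjusted model, which remains the answer to objective 4 and the comparison with the cited cytokine study. State that any claim of prognostic value beyond performance status will rest on the adjusted hazard ratio, and that neither model supports a claim of treatment-predictive value.

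The cost is one sentence in the plan and one degree of freedom per model, with no new data. The lost degree of freedom will be felt more at week 12, where fewer samples are likely, so the number of patients and events should be shown with each model. Naming the covariate now also prevents it from being chosen after the results are seen.

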16.0 MULTICENTER REGULATORY REQUIREMENTS

Washington University requires that each participating site sends its informed consent document to be reviewed and approved by the Washington University Regulatory Coordinator (or designee) prior to IRB/IEC submission.

Site activation is defined as when the secondary site has received official written documentation from the coordinating center that the site has been approved to begin enrollment. At a minimum, each participating institution must have the following documents on file at Washington University prior to study activation:

- Documentation of IRB approval of the study in the form of a letter or other official document from the participating institution's IRB. This documentation must show which version of the protocol was approved by the IRB.
- Documentation of IRB approval of an informed consent form. The consent must include a statement that data will be shared with Washington University, including the Quality Assurance and Safety Monitoring Committee (QASMC), the DSMC (if applicable), and the Washington University study team.
- Documentation of FWA, signed FDA Form 1572 (if applicable), and signed and dated the CVs of all participating investigators.
- Protocol signature page signed and dated by the investigator at each participating site.

The coordinating center is responsible for disseminating to the participating sites all study updates, amendments, reportable adverse events, etc. Protocol/consent modifications and IB updates will be forwarded electronically to the secondary sites within 4 weeks of obtaining Washington University IRB approval. Activated secondary sites are expected to submit protocol/consent/IB modifications to their local IRBs within 4 weeks of receipt, unless otherwise noted. Upon the secondary sites obtaining local IRB approval, documentation of such shall be sent to the Washington University study team within 2 weeks of receipt of approval.

Documentation of participating sites' IRB approval of annual continuing reviews, protocol amendments or revisions, all SAE reports, and all protocol violations/deviations/exceptions must be kept on file at Washington University.

The investigator or a designee from each institution must participate in a regular conference call to update and inform regarding the progress of the trial.

APPENDIX A: ECOG Performance Status Scale

Grade	Description
0	Normal activity. Fully active, able to carry on all pre-disease performance without restriction.
1	Symptoms, but ambulatory. Restricted in physically strenuous activity, but ambulatory and able to carry out work of a light or sedentary nature (e.g., light housework, office work).
2	In bed <50% of the time. Ambulatory and capable of all self-care, but unable to carry out any work activities. Up and about more than 50% of waking hours.
3	In bed >50% of the time. Capable of only limited self-care, confined to bed or chair more than 50% of waking hours.
4	100% bedridden. Completely disabled. Cannot carry on any self-care. Totally confined to bed or chair.
5	Dead.

APPENDIX B: New York Heart Association (NYHA) Functional Classification

NYHA Class	Symptoms
I	No symptoms and no limitation in ordinary physical activity, e.g., shortness of breath when walking, climbing stairs, etc.
II	Mild symptoms (mild shortness of breath and/or angina) and slight limitation during ordinary activity.
III	Marked limitation in activity due to symptoms, even during less-than-ordinary activity, e.g., walking short distances (20-100 m). Comfortable only at rest.
IV	Severe limitations. Experiences symptoms even while at rest. Mostly bedbound patients.

The Criteria Committee of the NYHA, Nomenclature and Criteria for Diagnosis of Diseases of the Heart and Great Vessels. 9th ed. Boston, Mass: Little, Brown & Co; 1994:253-256.

APPENDIX C: Medication Diary – Cycle 1

Today's Date: _____

Cycle 1

Agent: Pazopanib

Patient Name: _____

Study ID# 201501057

1. Take pazopanib by mouth under fasting conditions (at least one hour before or two hours after a meal).
2. Take pazopanib with a glass of water and drink the glass of water in as little time as possible.
3. Record the date, time and amount of drug taken. Write "1-200mg", "2-200mg", "3-200mg", or "4-200mg."
4. If you forgot to take your dose, do not take that dose. Restart pazopanib at the next scheduled dose.
5. If you vomit or notice any side effects, list in the comments section. Do not re-take a dose after vomiting.
6. Return this form and used pill bottles to your study coordinator when you go to your next appointment.

Important Dosing Instructions: Slowly increase the dose when you first start taking pazopanib.

First 4 days (Cycle 1, Days 1-4): Take **one 200-mg pill** in the morning, and **one 200-mg pill** in the evening.

Next 4 days (cycle 1, Days 5-8): Take **two 200-mg pills** in the morning, and **two 200-mg pills** in the evening.

Cycle 1, Day 9 and beyond: Take **four 200-mg pills** in the morning. *Do not take drug in the evening.*

Dose changes: If you experience side effects, you may be asked to discontinue or reduce the dose.

Day	Date	Morning		Evening		Comments
		Pill # and mg	Time Taken	Pill # and mg	Time Taken	
1						
2						
3						
4						
5						
6						
7						
8						
9						
10						
11						
12						
13						
14						
15						
16						
17						
18						
19						
20						
21						
22						

23					
24					
25					
26					
27					
28					

APPENDIX D: Medication Diary – Cycle 2 & Beyond (200 mg)

Today's Date: _____

Cycle: _____

Agent: Pazopanib

Patient Name: _____

Study ID# 201501057

1. Take pazopanib by mouth under fasting conditions (at least one hour before or two hours after a meal).
2. Take pazopanib with a glass of water and drink the glass of water in as little time as possible.
3. Record the date, time and amount of drug taken. Write "4-200mg", "3-200mg", "2-200mg" or "1-200mg."
4. If you forgot to take your dose, do not take that dose. Restart pazopanib at the next scheduled dose.
5. If you vomit or notice any side effects, list in the comments section. Do not re-take a dose after vomiting.
6. Return this form and used pill bottles to your study coordinator when you go to your next appointment.

Important Dosing Instructions: Take ____ **200-mg pills** in the morning or appropriate dose as instructed by physician.

Do not take drug in the evening.

Dose changes: If you experience side effects, you may be asked to discontinue or reduce the dose.

Day	Date	Morning		Comments
		Pill # and mg	Time Taken	
1				
2				
3				
4				
5				
6				
7				
8				
9				
10				
11				
12				
13				
14				
15				
16				
17				
18				
19				
20				
21				
22				
23				
24				
25				

26				
27				
28				

Medication Diary – Cycle 2 & Beyond (200 mg and/or 400 mg)

Today's Date: _____

Cycle: _____

Agent: Pazopanib

Patient Name: _____

Study ID# 201501057

1. Take pazopanib by mouth under fasting conditions (at least one hour before or two hours after a meal).
2. Take pazopanib with a glass of water and drink the glass of water in as little time as possible.
3. Record the date, time and amount of drug taken. Write "2-400mg" or 3-200mg, 2-200mg or 1-200mg.
4. If you forgot to take your dose, do not take that dose. Restart pazopanib at the next scheduled dose.
5. If you vomit or notice any side effects, list in the comments section. Do not re-take a dose after vomiting.
6. Return this form and used pill bottles to your study coordinator when you go to your next appointment.

Important Dosing Instructions: Take _____ **400-mg pills** and _____ **200-mg pills** in the morning. *Do not take drug in the evening.*

Dose changes: If you experience side effects, you may be asked to discontinue or reduce the dose.

Day	Date	Morning		Comments
		Pill # and mg	Time Taken	
1				
2				
3				
4				
5				
6				
7				
8				
9				
10				
11				
12				
13				
14				
15				
16				
17				
18				
19				
20				
21				
22				
23				
24				
25				
26				
27				
28				

APPENDIX E: FACT-G7

Below is a list of statements that other people with your illness have said are important. **Please circle or mark one number per line to indicate your response as it applies to the past 7 days.**

		Not at all	A little bit	Some- what	Quite a bit	Very much
GP1	I have a lack of energy	0	1	2	3	4
GP4	I have pain.....	0	1	2	3	4
GP2	I have nausea.....	0	1	2	3	4
GE6	I worry that my condition will get worse.....	0	1	2	3	4
GF5	I am sleeping well	0	1	2	3	4
GF3	I am able to enjoy life	0	1	2	3	4
GF7	I am content with the quality of my life right now	0	1	2	3	4
